9.5.2 Secondary Variables

Secondary efficacy parameters will be ranked as follows:

- 1) GOS-E at Month 6,
- 2) Mortality at Month 6 in mITT population (comparison of incidence of death),
- 3) GOS at Month 3,
- 4) GOS-E at Month 3,
- 5) Mortality at Month 1 in mTT population (comparison of incidence of death),
- 6) SF-36 mental composite score at Month 6,
- 7) SF-36 physical composite score at Month 6
- 8) SF-36 mental composite score at Month 3, and
- 9) SF-36 physical composite score at Month 3.

No confirmatory claims can be based on variables that have a rank lower than or equal to the variable whose null hypothesis was the first that could not be rejected at the p<0.05 significance level.

9.5.2.1 Mortality at Month 1, Month 6

These efficacy variables are obtained by collecting the survival status from the date of injury (Day 1 of the study) until Day 30 (Month 1) and Day 180 (Month 6) respectively as lost to follow-up, consent withdrawn, alive, dead or other. Every effort will be made to ascertain the survival status of subjects with status other than dead or alive, but in the absence of further information these observations will be omitted from the analysis. The 1-month mortality rate will be defined as the proportion of subjects at risk in the mITT population (subjects for whom the survival status at Day 30 is known) who died on or before Study Day 30. Similarly, the 6-month mortality rate will be defined as the proportion of subjects at risk in the mITT population who died on or before Study Day 180.

The hypothesis that the mortality rate observed in each treatment group is the same will be tested using the Fisher's Exact test.

$$\begin{array}{ll} \text{Null Hypothesis:} & H_0: p_1 = p_2 \\ \text{Alternative Hypothesis:} & H_1: p_1 \neq p_2 \end{array}$$

where p_1 = proportion of deaths in the BHR-100 treated group and p_2 = proportion of deaths in the placebo treated group.

A 2-sided, 5% significance level will be used to test the null hypothesis. If rejected ($p < 0.05$), it will be concluded that there is a statistically significant difference in the proportion of deaths between the 2 treatment groups.

In addition to the formal inference testing discussed above, 2-sided 95% confidence intervals for the difference in the proportion of deaths between BHR-100 and placebo treatment groups will be calculated.

Summaries of mortality at Months 1 and 6 will be presented for both the mITT and PP populations.

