Subjects without a GOS response assessment at Month 6 but who have a death date from the Death Report eCRF within 6 months + 28 days of their randomization date (calculated as death date – randomization date + 1 \leq 208) will be assigned a Month 6 GOS response of Dead. Similarly, subjects without a GOS response assessment at Month 3 but who have a death date from the Death Report eCRF within 3 months + 28 days of their randomization date (calculated as death date – randomization date + 1 \leq 118) will be assigned a Month 3 GOS response of Dead.

Secondary Endpoint: Mortality at Month 1

Survival status from the date of injury (Day 1 of the study) until Day 30 (Month 1) will be monitored and recorded as lost to follow-up, consent withdrawn, alive, dead or other. Only subjects with a mortality assessment post-injury of alive or dead will be used in the assessment of mortality.

Secondary Endpoint: Mortality at Month 6

Survival status from the date of injury (Day 1 of the study) until Day 180 (Month 6) will be monitored and recorded as lost to follow-up, consent withdrawn, alive, dead or other. Only subjects with a mortality assessment post-injury of alive or dead will be used in the assessment of mortality.

Time to death

The time to death (in days) will be defined as:

$$\text{Date of death} - \text{date of TBI} + 1$$

If a subject does not die during the conduct of the study, they will be censored at the earliest (minimum) of their Month 6 GOS assessment date and end of study date, and censor time (in days) will be defined as:

$$\text{Minimum(month 6 GOS assessment date, end of study date)} - \text{date of TBI} + 1$$

Since subjects were not followed for death after their Month 6 GOS assessment, subjects who have a death recorded after the assessment will be censored on the date of their Month 6 assessment.

Exploratory Endpoint: CPP

The following formulae are used to derive CPP:

$$\text{Mean Arterial Pressure (MAP)} = \frac{2}{3} \text{ diastolic BP} + \frac{1}{3} \text{ systolic BP};$$

$$\text{CPP} = \text{MAP} - \text{ICP}.$$

MAP will be recorded as missing if either systolic BP and/or diastolic BP measurements are not recorded. CPP will be calculated where MAP and ICP have both been recorded; if either is missing the CPP will be recorded as missing.

Exploratory Endpoint: TIL

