9.5.3 Exploratory Variables

9.5.3.1 Time to Death

The actual time to death will be analyzed for the mITT population.

If a subject does not die during the conduct of the study, they will be censored at their Month 6 GOS assessment or end of study date, whichever comes first.

The LIFETEST procedure in SAS® will be used to produce Kaplan-Meier plots and estimates of 25th, 50th, and 75th quartiles and corresponding 95% confidence limits of the median time to death. The 2 treatment groups will be compared using a 2-sided log-rank test. Examination of the point estimates will indicate the direction of the treatment difference. The cumulative percent mortality based on the Kaplan-Meier survival probability estimates will be plotted for each treatment group.

The time to death (in days) will be further analyzed using a Cox proportional hazard model. The comparison of the treatment effect on the time to death will be based on the hazard ratio (HR) from the Cox regression model using the PHREG procedure in SAS®. Estimates of HR and 95% confidence limits will be presented. The model will include the same terms as the primary efficacy analysis, namely treatment, region, age, GCS motor score, pupil response, and CT classification.

The Cox proportional hazards model is a standard model used in failure time analysis. Compared to parametric analyses, its assumptions are fairly unspecified and will therefore yield robust estimates of the treatment effect. The model will be applied using the Efron approach for handling ties, since this approach is known to give a reasonable approximation of the exact likelihood in the presence of ties and is computationally faster when large amounts of data are being analyzed.

9.5.3.2 Comparison of CT scans at admission and Day 6

A CT scan will be performed before randomization (Day 1) and once again at Day 6 ± 1 day post-injury to assess the progression of lesion volume and brain edema. The findings by the Central Reader will be classified in accordance with the Marshall classification:

- Diffuse injury I - no visible pathology (CT class I),
- Diffuse injury II (CT class II),
- Diffuse injury III – swelling (CT class III),
- Diffuse injury IV – shift (CT class IV),
- Evacuated mass lesion (CT class V),
- Non-evacuated mass lesion (CT class VI).

A shift summary of CT classification from Baseline to Day 6 will be presented by treatment group.

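### The ranked mortality tests leave out the baseline covariates used in the primary model, and no sensitivity analysis covers patients of unknown survival status

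*SAP*

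**What the plan says.** SAP Section 9.5.2 places mortality at ranks 2 and 5, the former as "2) Mortality at Month 6 in mITT population (comparison of incidence of death" and so on. The chain stops at the first endpoint that misses p<0.05.

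Section 9.5.2.1 restricts the Month 1 denominator to "subjects for whom the survival status at Day 30 is known", and treats Month 6 in the same way. Sites must first try to establish every patient's status; failing that, "in the absence of further information these observations will be omitted from the analysis". Section 5 repeats the rule: "Only subjects with a mortality assessment post-injury of alive or dead will be used in the assessment of mortality".

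On the test: "The hypothesis that the mortality rate observed in each treatment group is the same will be tested using the Fisher's Exact test". And: "A 2-sided, 5% significance level will be used to test the null hypothesis". Protocol Section 8.4.1 also names Fisher.

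Section 9.5.3.1 analyses the same deaths by Kaplan-Meier, log-rank and Cox regression. For the Cox model, "The model will include the same terms as the primary efficacy analysis, namely treatment, region, age, GCS motor score, pupil response, and CT classification". All of this is exploratory and outside the ranking.

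Neither document plans a sensitivity analysis for unknown survival status. The observed-values check in Section 5 and the remark there about minimal missing data concern the primary GOS endpoint.

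**The concern.** There are two separate issues.

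**Covariates.** Region, age, motor score, pupil response and CT class are collected for everyone and used in the primary model. The ranked mortality test ignores them, including region, the randomization stratum. A miss at rank 2 removes confirmatory status from Month 6 mortality and from the seven endpoints below it, so avoidable power loss there is costly.

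**Unknown status.** A patient whose death is recorded before contact would have been lost is counted. A patient lost while alive, and never traced, is removed from the denominator. The removal therefore depends partly on outcome. The trial has a plausible route to selective removal: under Protocol Section 10.3, a patient who regains capacity and declines to continue is withdrawn, and withdrawn consent is one of the omitted statuses. Such patients are alive and recovering. If loss differs between arms, the comparison shifts.

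**Working it through.** **Inputs from the documents.** 1180 patients, 590 per arm, common odds ratio 1.5 for GOS (SAP 3.1); placebo vegetative state and death combined 29% (SAP 3.1); mortality of 20% to 39% in severe TBI (Protocol 1.1); two-sided 5% level.

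**Assumed, because the documents are silent.** Odds ratio 1.5 for death; placebo mortality 20-29%; loss 0-10%; covariate strength expressed as AUC.

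**The plan's own figure.** No power is stated for mortality. The 590 per arm comes from the GOS calculation, N = 12(z_α/2 + z_β)² / [ln(OR)² (1 − Σp̄³)]. Odds ratio 1.5 turns 31/21/19/29% into about 40.3/21.6/16.7/21.4%. The averages give Σp̄³ ≈ 0.0766. Then N = 12 × (2.576 + 1.282)² / (0.4055² × 0.9234) ≈ 1176, which agrees with 1180.

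**Fisher power for mortality.** Drug-arm risk at 25% placebo mortality: odds 0.25/0.75 = 0.333; divided by 1.5 = 0.222; risk 0.222/1.222 = 18.2%. Exact results at 590 per arm:

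| Placebo / drug | Fisher power | Uncorrected z-test | Fisher's true size |
|---|---|---|---|
| 20% / 14.3% | 71.7% | 74.1% | 4.2% |
| 25% / 18.2% | 79.5% | 81.3% | 4.3% |
| 29% / 21.4% | 83.8% | 85.3% | 4.3% |

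Fisher's conservatism alone thus costs about 1.5 to 2.4 points.

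**Adjusted logistic test against Fisher.** Both were applied to known-status patients, in 1500 to 2000 simulated trials per scenario with 0-10% non-informative loss:

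| Placebo mortality | AUC | Fisher | Adjusted logistic |
|---|---|---|---|
| 20% | about 0.65 | 71-72% | 75-76% |
| 20% | 0.77 | 70-72% | 79-81% |
| 25% | about 0.65 | 79-80% | 82-83% |
| 25% | about 0.78 | 78-80% | 87-88% |
| 29% (5% loss only) | 0.66 | 83% | 87% |
| 29% (5% loss only) | 0.78 | 84% | 92% |

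Scenario by scenario the gain is about 3 to 10 points. These figures are at the favourable end, because the prognostic score entered the model as one correctly specified term. With the planned covariates entered as separate terms at similar or weaker strength, the gain stays within about 2 to 9 points, and I use that range. An assumed AUC near 0.85 would give more (78.7% to 92.4% at 25% mortality), but the documents do not support choosing it. Raising loss from 0 to 10% moved Fisher's power by only about 1 point, so omission is not the main source of lost power.

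**Known-status proportion against Kaplan-Meier.** Take N patients, D recorded deaths and C lost alive at times c_i. The Kaplan-Meier risk F at Day 180 satisfies F = [D + Σ(1 − S(180)/S(c_i))]/N. Because S(c_i) ≤ 1, each term is at most 1 − S(180) = F. So F ≤ (D + C·F)/N, hence F ≤ D/(N − C), the known-status proportion. No exception occurred in 3000 simulated data sets.

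**Size of the excess under non-informative loss.** Example: true mortality 25%, 5% of patients given a loss time uniform over Days 15-180, about 62% of deaths by Day 30. Some die before their loss time, so 3.97% are omitted. Known alive: 0.95 × 0.75 = 0.7125. Known dead: 1 − 0.0397 − 0.7125 = 0.2478. Reported: 0.2478/0.9603 = 25.8%. Over true mortality 25% and 29% and three death-timing patterns, the excess is 0.2 to 0.4 points at 2% loss, 0.6 to 0.9 at 5% and 1.2 to 1.9 at 10%.

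**Informative loss.** In the same example true mortality lies between 24.8% (all omitted patients survive) and 0.2478 + 0.0397 = 28.8% (all die). The reported 25.8% can therefore be too high or too low.

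**Unequal loss.** With equal true mortality of 25%, losing 10% in one arm and 2% in the other gives 26.7% against 25.3%, a false difference of 1.4 points. The standard error of the difference is √(2 × 0.25 × 0.75/590) = 2.5 points.

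**The case against.** Fisher on known status is a valid test when loss is equal and non-informative, and is slightly conservative. Kaplan-Meier, log-rank and adjusted Cox results will be reported anyway, so follow-up time is not discarded. The shell for Table 14.2.5.1 shows lost, withdrawn and other patients by arm, so imbalance would be visible and a reader could compute bounds. Sites must try to trace every patient. All of this stands, and it limits the point to an improvement.

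A reader might infer three stronger things that the documents do not support.

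- *The plan overstates mortality.* That is certain only relative to Kaplan-Meier on the same patients. A patient lost on Day 40 who dies untraced on Day 60 is omitted, not counted, so informative loss can reverse the bias. Follow-up for death also ends at the Month 6 visit, which may fall up to 28 days early; counting such patients as alive at Day 180 works in the opposite direction.
- *Omission is what weakens the test.* Its cost is about 1 point of power. The rest comes from not adjusting and from Fisher's conservatism.
- *The planned Cox model should carry the rank.* One Cox model followed to Month 6 does not test Month 1 mortality. It replaces incidence of death by a hazard ratio and itself assumes non-informative censoring.

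**Conclusion.** The point holds as a cheap improvement. The ranked mortality tests ignore prognostic data that the primary model already uses, and unknown status has no sensitivity analysis. The likely cost is about 2 to 9 points of power, given odds ratio 1.5, 590 per arm, 20-29% placebo mortality and covariates of weak to moderate strength; none of these is specified for mortality in the documents. At the weak end most of the gain is simply the removal of Fisher's conservatism.

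The bias in the reported rates is small if loss is small, equal and non-informative. Its direction against the true rate is not guaranteed. Nothing here shows an invalid test or a contradiction in the plan.

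**What to change.** Before unblinding, amend SAP 9.5.2.1 as follows.

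1. Keep both endpoints as incidence of death, by Day 30 and by Day 180.
2. Make the ranked test at each time point a comparison adjusted for region, age, GCS motor score, pupil response and CT class, for example logistic regression in patients of known status. Extend the Section 5 covariate imputation to it; at present that rule covers only the primary efficacy analyses, so patients with a missing covariate could drop out.
3. Report Kaplan-Meier Day 30 and Day 180 rates and their difference in all mITT patients, censored at last known alive.
4. Add a best/worst-case analysis for patients of unknown status.
5. Keep Fisher on known status as a sensitivity analysis, and leave the Cox model exploratory.

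The cost is a further departure from Protocol 8.4.1, to be listed in SAP 1.1. There is a precedent in that section, where the protocol's Wilcoxon test for GOS-E was replaced by a proportional odds model. Programming additions are small: the shell for Table 14.2.5.5 has quartiles and a log-rank p-value but no Day 30 or Day 180 rates. An adjusted odds ratio would stand beside the simple difference in proportions, and the text should say which carries the test.

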9.5.2.4 Quality of Life: SF-36

During the conduct of the study, the SF-36 health survey will be administered at Months 3 and 6 to assess quality of life with respect to health status. Since a baseline SF-36 is not assessed prior to study treatment, the analyses of the SF-36 will compare mean SF-36 scores at Month 3 and 6 between treatment groups.

The SF-36 consists of 36 questions that are grouped into eight scaled scores. These scores are the weighted sums of the questions in their section. Each scale is directly transformed into a 0-100 scale on the assumption that each question carries equal weight.

For each scale, a simple mean imputation of missing data with a restriction to cases where the subject has completed at least 50% of the items of that scale (the “half-scale” rule) will be used.

The eight sections are as follows:

- Vitality,
- Physical functioning,
- Bodily pain,
- General health perceptions,
- Physical role functioning,
- Emotional role functioning,
- Social role functioning, and
- Mental health.

Summary statistics for the 8 scales and the physical and mental composite summary scores will be presented for each treatment group.

In addition to summarizing the data, the physical and mental composite summary scores at Month 3 and 6 will be analyzed using an analysis of covariance (ANCOVA) model including treatment group.

The null hypothesis that the mean physical and mental summary scores are the same for both treatment groups (BHR-100 and placebo) will be tested against the 2-sided alternative hypothesis that the mean physical and mental summary scores are different in each treatment group, at the 0.05 significance level.

The least square means for the treatment groups, difference in least square means between the treatment groups, effect size calculated as the absolute difference in least square means between BHR-100 and placebo divided by the root mean square, and p-value for difference between treatment groups will be presented.

A 2-sided, 5% significance level will be used to test the null hypothesis. If rejected at the 5% level ($p < 0.05$), it will be concluded that there is a statistically significant difference in the relevant summary score between the 2 treatment groups. The magnitude of the summary statistics will be examined to determine the direction of the treatment difference.

Diagnostic residual plots will be evaluated to test for violations of normality. If the normality assumption for the model is not met, the null hypothesis that the mean physical and mental summary scores are the same in each treatment group will be tested using the 2-sided Wilcoxon Rank-Sum test, an unstratified non-parametric test, which can be obtained from the NPAR1WAY procedure in SAS®.

9.5.3 Exploratory Variables

9.5.3.1 Time to Death

The actual time to death will be analyzed for the mITT population.

If a subject does not die during the conduct of the study, they will be censored at their Month 6 GOS assessment or end of study date, whichever comes first.

The LIFETEST procedure in SAS® will be used to produce Kaplan-Meier plots and estimates of 25th, 50th, and 75th quartiles and corresponding 95% confidence limits of the median time to death. The 2 treatment groups will be compared using a 2-sided log-rank test. Examination of the point estimates will indicate the direction of the treatment difference. The cumulative percent mortality based on the Kaplan-Meier survival probability estimates will be plotted for each treatment group.

The time to death (in days) will be further analyzed using a Cox proportional hazard model. The comparison of the treatment effect on the time to death will be based on the hazard ratio (HR) from the Cox regression model using the PHREG procedure in SAS®. Estimates of HR and 95% confidence limits will be presented. The model will include the same terms as the primary efficacy analysis, namely treatment, region, age, GCS motor score, pupil response, and CT classification.

The Cox proportional hazards model is a standard model used in failure time analysis. Compared to parametric analyses, its assumptions are fairly unspecified and will therefore yield robust estimates of the treatment effect. The model will be applied using the Efron approach for handling ties, since this approach is known to give a reasonable approximation of the exact likelihood in the presence of ties and is computationally faster when large amounts of data are being analyzed.

9.5.3.2 Comparison of CT scans at admission and Day 6

A CT scan will be performed before randomization (Day 1) and once again at Day 6 ± 1 day post-injury to assess the progression of lesion volume and brain edema. The findings by the Central Reader will be classified in accordance with the Marshall classification:

- Diffuse injury I - no visible pathology (CT class I),
- Diffuse injury II (CT class II),
- Diffuse injury III – swelling (CT class III),
- Diffuse injury IV – shift (CT class IV),
- Evacuated mass lesion (CT class V),
- Non-evacuated mass lesion (CT class VI).

A shift summary of CT classification from Baseline to Day 6 will be presented by treatment group.

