3.1 Sample Size Considerations

The primary efficacy measurement for this study is GOS at 6 months after injury; see section 4.1.

For the purposes of the analysis and sample size calculation, the first 2 categories of the GOS (vegetative state and dead) will be combined. Based on the 6-month GOS outcome distribution from the head injury population with GCS 3-8 in the previous TBI Phase 3 trials in the International Mission for Prognosis and Analysis of Clinical Trials in TBI Project (IMPACT) Database, it is assumed that the following GOS responses will be observed at 6 months, in subjects treated with placebo: 31% good recovery, 21% moderate disability, 19% severe disability, and 29% vegetative state or dead (Lu, 2011).

A sample size of 1,180 subjects receiving study drug (590 in each treatment group) will be needed to detect a common odds ratio of 1.5, of improvement in GOS at 6 months in BHR-100 compared to placebo, at 90% power and a significance level of 0.01 (2-sided). This calculation used the sample size equation for comparing 2 groups of ordinal data using the technique of ordinal logistic regression proposed by Whitehead (1997).

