3.2 Randomization

Subjects will be randomized to either BHR-100 or placebo on a 1:1 ratio, using an IWRS. The randomization will be stratified by geographic region of the site locations in order to avoid imbalance in the distribution of treatment groups within regions.

The following countries are planned to be involved in the study: Argentina, Austria, Belgium, China, Czech Republic, Finland, France, Germany, Hungary, Israel, Italy, Malaysia, Netherlands, Romania, Russia, Singapore, Spain, Taiwan, Thailand, United Kingdom, and United States. Additional countries may be considered.

These countries will be grouped into the following regions: North America (US), Europe (Austria, Belgium, Czech Republic, Finland, France, Germany, Hungary, Israel, Italy, Netherlands, Romania, Russia, Spain and UK), Asia (China, Malaysia, Singapore, Taiwan, and Thailand) and South America (Argentina).

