9 STATISTICAL METHODS

All analyses and reporting of study results will be conducted using SAS V9.1.3 In addition EAST will be used to adjust for the interim analysis.

All variables will be presented using appropriate descriptive statistics according to the variable nature:

- Continuous variables: number of non-missing observations, mean, standard deviation , minimum, first quartile (Q1), median, third quartile (Q3), maximum,
- Categorical variables: number of non-missing observations, absolute and relative frequency (n and percentages (%)),
- Time-to-event variables: number of non-missing observations, number and percentage of censored observations, first quartile, median (and 95% CI), third quartile, and Kaplan-Meier survival curves.

The behavior over time of continuous variables will be analyzed by presenting descriptive statistics for each time point and the difference compared to baseline (actual values and change from baseline). The behavior over time of categorical data will be analyzed by presenting the descriptive statistics for each time point and the shift compared to baseline.

The decimal places for summary statistics and percentages will be as follows:

- Precision of data + 2 decimal places (dp) for standard deviations,
- Precision of data + 1 dp for means, medians and quartiles,
- Same precision as data for minimum and maximum,
- 1 dp for percentages except when the percentage is 100% in which case no dp would be presented, and

The primary and confirmatory efficacy analyses will be 2-sided and conducted at a 1% significance level. All secondary efficacy tests will be 2-sided and conducted at a 5% significance level.

The randomization will be stratified by region. This variable will be included as a covariate in the primary and secondary GOS efficacy analyses.

Secondary efficacy analyses will be conducted in ranked order as listed in Section 9.5.2 with the understanding that no confirmatory claims can be based on variables that have a rank lower than or equal to that variable whose null hypothesis was the first that could not be rejected at the $p<0.05$ significance level.

All exploratory analyses will be considered supportive in nature, and therefore no adjustment will be made for multiple testing of exploratory variables.

All data will be included in subject data listings for all subjects in the mITT population.

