 [Update the footnotes to reflect Month 1 timepoint.]

Table 14.2.5.3 Summary and Analysis of Mortality at Month 6 (PP Population)

Table 14.2.5.4 Summary and Analysis of Mortality at Month 1 (PP Population)

Table 14.2.5.5 Summary and Kaplan-Meier Analysis of Time to Death¹ (days) (mITT Population)

	Statistic	BHR-100 (N=xx)	Placebo (N=xx)
Kaplan-Meier Estimates			
	Total Deaths	xx	xx
	Total Censored	xx	xx
	25 th percentile	xx	xx
	Median (95% CI)	xx (xx , xx)	xx (xx , xx)
	75 th percentile	xx	xx
Treatment Difference from Placebo ²		p=0.xxx	

¹ Time to Death (in days) = Date of death/date of last contact (for censored records) - date of TBI + 1.

² P-value is based on Log-Rank test.

Source: Listing 16.2.6.3.1.

Program: xxxxxxx.sas, Output: xxxxxxx.rtf, Generated on: DDMONYYYY xx:xx, Page x of x

[Note to Programmer: The K-M estimates are those obtained from PROC LIFETEST.

The log-rank test is fitted in SAS using the following syntax:

```
PROC LIFETEST DATA=<dataset name>;
  TIME WKS*CENS(1 - censoring indicator);
  STRATA TREATMENT;
RUN; ]
```

Table 14.2.5.6 Summary of Cox Proportional Hazards Analysis of Time to Death (days) (mITT Population)

Factor/Covariate ¹	Hazard Ratio ¹	95% Confidence Limits	P-value
Treatment Group (BHR-100 vs. Placebo)	x.xxx	(x.xxxx, x.xxxx)	0.xxx
Region (North America vs. Europe)	x.xxx	(x.xxxx, x.xxxx)	0.xxx
Region (Asia vs. Europe)	x.xxx	(x.xxxx, x.xxxx)	0.xxx
Region (South America vs. Europe)	x.xxx	(x.xxxx, x.xxxx)	0.xxx
Age	x.xxx	(x.xxxx, x.xxxx)	0.xxx
GCS Motor Score (3 vs. 1/2)	x.xxx	(x.xxxx, x.xxxx)	0.xxx
GCS Motor Score (4 vs. 1/2)	x.xxx	(x.xxxx, x.xxxx)	0.xxx
GCS Motor Score (5/6 vs. 1/2)	x.xxx	(x.xxxx, x.xxxx)	0.xxx
Pupil Response (Bilateral vs. Unilateral/No Reactive Pupils/Not Testable)	x.xxx	(x.xxxx, x.xxxx)	0.xxx
CT Classification (I/II vs. V/VI)	x.xxx	(x.xxxx, x.xxxx)	0.xxx
CT Classification (III vs. V/VI)	x.xxx	(x.xxxx, x.xxxx)	0.xxx
CT Classification (IV vs. V/VI)	x.xxx	(x.xxxx, x.xxxx)	0.xxx

¹ For factors the last level is taken as the reference level. Marshall CT classification was used.

Source: Listings 16.2.6.1.6 and 16.2.6.3.1.

Program: xxxxxxx.sas, Output: xxxxxxx.rtf, Generated on: DDMONYYYY xx:xx, Page x of x

[Note to Programmer: Indicator variables or PROC TPHREG (which has a CLASS statement) will need to be created for the factors with more than 2 levels (Region, GCS motor score, Pupil Response and CT classification).

```

proc tphreg data=<dataset>;

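### The exploratory log-rank test of time to death is unstratified although randomisation is stratified by region; the test is valid, but it gives up a little power if mortality differs between regions

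*SAP*

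**What the plan says.** Region is the only stratification factor. SAP 3.2: "The randomization will be stratified by geographic region of the site locations". The four strata are North America, Europe, Asia and South America, with 1:1 allocation.

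SAP 9.5.3.1 gives two analyses of time to death in the mITT population:

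- Kaplan-Meier estimates with a test: "The 2 treatment groups will be compared using a 2-sided log-rank test". No stratification is named. The shell for Table 14.2.5.5 footnotes its p-value as log-rank, and its code note reads "STRATA TREATMENT", with no region term. Text and code agree.
- A Cox model, reported in Table 14.2.5.6: "The model will include the same terms as the primary efficacy analysis, namely treatment, region, age, GCS motor score, pupil response, and CT classification". The section says that the treatment comparison rests on the hazard ratio from this model.

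The general statement on region in SAP 9 covers only the outcome scale: "This variable will be included as a covariate in the primary and secondary GOS efficacy analyses". Time to death sits under the exploratory variables (9.5.3), and SAP 9 says "All exploratory analyses will be considered supportive in nature". The ranked mortality endpoints in 9.5.2 use Fisher's exact test. Protocol 8.4.1 names only Kaplan-Meier and Cox methods for time to death, so the log-rank test enters with the SAP.

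**The concern.** When randomisation is balanced within region and regions have different death rates, an unstratified log-rank test pools patients at unequal risk into one risk set. Two things follow. The treatment contrast is pulled slightly towards no effect, because the higher-risk regions deplete faster. The variance formula also ignores the balance that stratified randomisation created, so it is somewhat too large. Both cost power.

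Region is in the primary proportional odds model, the sliding-dichotomy CMH test, the dichotomised model and the Cox model for this same variable. The log-rank test beside that Cox model is an exception with no stated reason. What is at stake is modest: a supportive p-value that is a little less sensitive than it could be. It is also harder to compare with the Cox p-value, because the two differ by region and by four further covariates at once.

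**Working it through.** **What the plan states.** There is no power or event count for time to death. The only design figure is the total of 1180 for the primary GOS analysis (SAP 3.1), "needed to detect a common odds ratio of 1.5" with 90% power at two-sided 0.01. It is reproduced here only to confirm the sample size carried into the simulations.

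Whitehead's formula for 1:1 allocation: N = 12 (z_(1-α/2) + z_power)² / [ln(OR)² (1 − Σ p̄³)].

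- Placebo distribution: 31/21/19/29%. Applying OR 1.5 gives 40.3/21.6/16.7/21.4% on BHR-100.
- Averages: 35.6/21.3/17.8/25.2%, so 1 − Σ p̄³ ≈ 0.923.
- N ≈ 12 × (2.576 + 1.282)² / (0.1644 × 0.923) ≈ 1176 at α = 0.01, and 1180 at the final nominal 0.0098. The plan's figure reproduces.

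**The two tests.** Unstratified: Z = (O − E)/√V from one pooled risk set. Stratified: Z = Σ(O_r − E_r)/√ΣV_r, summed over regions r. Both were computed on the same simulated trials and compared with ±1.96.

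**Common inputs.** 1180 patients, 1:1 within region, one hazard ratio across regions, follow-up to Month 6, two-sided 5%. Assumed, because the documents do not give them for this test: hazard ratio, regional shares, regional mortality and the 5% level. The 20-39% band is taken from Protocol 1.1, where it is a range across studies of severe TBI. It is not a spread between regions and is not stated to be six-month mortality.

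**Set A: HR 0.75, shares 25/40/25/10%, deaths front-loaded (Weibull shape 0.4), 4000 trials per setting.**

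| Regional mortality | Unstratified | Stratified | Gain (points) |
|---|---|---|---|
| spread across 20-39% | 68.7% | 69.4% | 0.7 |
| regions at 20% v 39% | 65.9% | 67.6% | 1.7 |
| regions at 25% v 33% | 68.7% | 68.7% | 0.0 |

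The two tests fell on opposite sides of 5% in 3-6% of trials. The simulation error of a paired difference is therefore about √(0.03/4000) = 0.27 to √(0.06/4000) = 0.39 points.

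**Set B: HR 0.70, exponential survival, 20,000 trials per setting.** Shares are in the order North America/Europe/Asia/South America. The last two columns are rejection rates with no treatment effect (HR 1).

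| Shares | Control mortality by region | Unstratified | Stratified | Gain (points) | Null, unstratified | Null, stratified |
|---|---|---|---|---|---|---|
| 25/45/25/5% | 20/26/33/39% | 83.58% | 83.91% | 0.3 | 5.28% | 5.44% |
| 25/45/25/5% | 20/20/39/39% | 81.36% | 82.62% | 1.3 | 4.71% | 5.11% |
| 25/45/25/5% | 10/25/50/50% | 83.44% | 86.38% | 2.9 | 3.84% | 5.12% |
| equal | 20/26/33/39% | 86.93% | 87.32% | 0.4 | 4.82% | 5.15% |
| equal | 20/20/39/39% | 85.92% | 86.94% | 1.0 | 4.34% | 4.94% |
| equal | 10/25/50/50% | 88.84% | 91.20% | 2.4 | 3.63% | 5.20% |

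The 10-50% rows are deliberately extreme and outside the quoted band. With 29% mortality in every region (3000 trials), power is 86.2% unstratified and 86.3% stratified, so stratifying costs nothing when regions are alike.

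**Cross-check.** Schoenfeld's formula for the first row, with 276.3 expected deaths: √276.3/2 × |ln 0.70| − 1.96 = 2.964 − 1.960 = 1.004, so power is 84.2%, close to the simulated 83.6% and 83.9%.

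**The case against.** The strongest reply is that the section already contains what is being asked for. The comparison is based on a Cox hazard ratio adjusted for region, age, GCS motor score, pupil response and CT classification, which is more adjustment than region alone. The endpoint is exploratory, it lies outside the ranked list, and 9.5.3.1 attaches no threshold or conclusion to the log-rank p-value, so disagreement between the two tests in 3-6% of trials overturns no decision. The gain is small and rests on assumed inputs; Set A's 0.7 points is only about two simulation standard errors. An unstratified p-value also matches the pooled curves it is printed with.

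All of this stands as a limit on importance. It does not give a reason to leave the stratum out: the p-value in Table 14.2.5.5 still ignores region, and including it costs nothing even when regions are alike. A footnote deals with the match to the curves.

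A reader might infer three stronger things that the documents and calculations do not support:

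- That the test is invalid because it ignores the stratification. Its null rejection rate is 4.3-5.3% within the 20-39% band and 3.6-3.8% at the extreme spread. Apart from simulation noise around 5%, any departure is on the conservative side.
- That the SAP breaks its own rule on region. That rule is confined to the GOS analyses, so this is an unexplained exception and not a contradiction.
- That mortality is known to differ by region. Nothing in either document says so.

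**Conclusion.** The point holds as a minor one. The log-rank test is unstratified in both text and code, while region is the sole randomisation stratum. The loss of power is about 0 to 1.7 points if regional mortality lies within an assumed 20-39%, reaches 2.4 to 2.9 points only under a deliberately extreme 10-50% spread, and is nil if regions are alike. These sizes rest on an assumed hazard ratio of 0.70 or 0.75, assumed regional shares and mortality, and a hazard ratio common to all regions. Type I error is not inflated. The primary analysis, the ranked secondary endpoints and the Cox hazard ratio are all unaffected.

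**What to change.** Before unblinding:

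- In SAP 9.5.3.1, specify the two-sided log-rank test as stratified by region.
- In the Table 14.2.5.5 code note, make region the stratum and treatment the compared group. Equivalently, take the score test from a Cox model with treatment only, region as stratum and discrete handling of ties. Keep a separate by-arm call for the Kaplan-Meier estimates and curves.
- Footnote in Table 14.2.5.5 that the p-value is region-stratified while the curves are pooled over regions.
- Keep the adjusted Cox hazard ratio as the main time-to-death comparison and say so in one sentence.

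The cost is a few words, a footnote and a line or two of code. The code note needs an edit in any case: its time variable is named for weeks, while SAP 5 and the table define time to death in days. SAP 1 describes this as the final version before database lock, so the change needs a dated amendment; choosing between the two tests after unblinding would be open to challenge.
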